## **Prohibited and Rescue Medications**

Prohibited medication/class of drug:	Usage:			
Additional investigational anticancer therapy concurrent with those under investigation in this study	Should not be given whilst the patient is on IP treatment			
mAbs against CTLA-4, PD-1, or PD-L1other than those under investigation in this study	Should not be given whilst the patient is on IP treatment through 90 days after the last dose of IP.			
Any concurrent chemotherapy, local therapy (except palliative radiotherapy for non-target lesions, eg, radiotherapy, surgery, radiofrequency ablation), biologic therapy, or hormonal therapy for cancer treatment	Should not be given whilst the patient is on IP treatment (including SoC). (Concurrent use of hormones for non-cancer-related conditions [eg, insulin for diabetes and hormone replacement therapy] is acceptable.)			
Immunosuppressive medications, including, but not limited to, systemic corticosteroids at doses exceeding 10 mg/day of prednisone or its equivalent, methotrexate, azathioprine, and tumor necrosis factor α blockers	Should not be given whilst the patient is on IP treatment (including SoC). (Use of immunosuppressive medications for the management of IP-related AEs or in patients with contrast allergies is acceptable. In addition, use of inhaled, topical, and intranasal corticosteroids is permitted.			
Live attenuated vaccines	Should not be given through 30 days after the last dose of IP (including SoC) during the study			

Rescue/supportive medication/class of drug:	Usage:		
Concomitant medications or treatments (eg, acetaminophen or diphenhydramine) deemed necessary by the Investigator to provide adequate prophylactic or supportive care, except for those medications identified as "prohibited" as listed above	To be administered as prescribed by the Investigator		
Best supportive care (including antibiotics, nutritional support, growth factor support, correction of metabolic disorders, optimal symptom control, and pain management [including palliative radiotherapy, etc])	Should be used when necessary for all patients		

## 8.0 STUDY PROCEDURES

## 8.1 Schedule of study procedures

Before study entry, throughout the study, and following study drug discontinuation, various clinical and diagnostic laboratory evaluations are outlined. The purpose of obtaining these detailed measurements is to ensure adequate safety and tolerability assessments. Clinical evaluations and laboratory studies may be repeated more frequently if clinically indicated. The Schedules of Assessments during the screening and treatment period is provided following the Protocol Synopsis.

# 8.1.1 Screening Phase

Screening procedures will be performed within 28 days of Day 1, unless otherwise specified. All subjects must first read, understand, and sign the IRB/REB/IEC-approved ICF before any study-specific screening procedures are performed. After signing the ICF, completing all screening procedures, and being deemed eligible for entry, subjects will be enrolled in the study. Procedures that are performed prior to the signing of the ICF and are considered standard of care may be used as screening assessments if they fall within the 28-day screening window.

### . TABLE 1: SCHEDULE OF STUDY ASSESSMENTS

Assessments to be performed at the times stipulated in the table and as clinically required in themanagement of the subject.	Screening	C1	C2	С3	C4	C5	C6	C7	C8	С9	C10	C11	C12	C13	Refer to Section
 						sment: ±									
Day	-28 to[contact]	141	169	197	225	253	281	309	337	
Week	-4 to +1	0	4	8	12	16	20	24	28	32	36	40	44	48	
Written informed consent/assignment of subject identification number	X														
Previous treatments for prostate cancer	X														
Formal verification of eligibility criteria	X														
Medical and surgical history	X														
Durvalumab and Tremelimumab Combination Administration j		X	X	X	X										Section 6.3.1
Durvalumab Administration(Mono therapy)				Xj	Xj	X	X	X	X	X	X	X	X	X	Section 6.3.1

Assessments to be performed at the times stipulated in the table and as clinically required in themanagement	Screening	C1	C2	СЗ	C4	C5	C6	C7	C8	С9	C10	C11	C12	C13	Refer to Section
of the subject.			Windo	w for ea	ch asses	sment:	±3 days	, windo	w for tu	mor ass	essment	: ±7 day	/S		
Day	-28 to [contact]	141	169	197	225	253	281	309	337	
Week	-4 to+1	0	4	8	12	16	20	24	28	32	36	40	44	48	
Physical examination a	X	X	X	X	X	X	X	X	X	X	X	X	X	X	
Weight	X	X	X	X	X	X	X	X	X	X	X	X	X	X	
Vital signs (pre-, during and post-infusion vital signs assessments) b	X	X	X	X	X	X	X	X	X	X	X	X	X	X	
Electrocardiogram c	X						As clin	ically in	dicated						
Adverse event/serious adverse event assessment	X	X	X	X	X	X	X	X	X	X	X	X	X	X	Section 10.1
Concomitant medications	X	X	X	X	X	X	X	X	X	X	X	X	X	X	Section 7.3
Palliative radiotherapy						As cli	inically i	ndicated	l						Section 7.3
ECOG performance status	X	X	X	X	X	X	X	X	X	X	X	X	X	X	
Serum chemistry (complete clinical chemistry panel including liver enzymes) d	X	X	X	X	X	X	X	X	X	X	X	X	X	X	

Assessments to be performed at the times stipulated in the table and as clinically required in themanagement of the subject.	Screening	C1	C2	С3	C4	C5	C6	C 7	C8	С9	C10	C11	C12	C13	Refer to Section
			Windo	w for ea	ch asses	sment:	±3 days	, windov	v for tu	mor ass	essment	: ±7 day	'S	•	
Day	-28 to[contact]	141	169	197	225	253	281	309	337	
Week	-4 to +1	0	4	8	12	16	20	24	28	32	36	40	44	48	
Thyroid function tests (TSH and T3 and fT4) e	X	X	X	X	X	X	X	X	X	X	X	X	X	X	
Hematology d	X	X	X	X	X	X	X	X	X	X	X	X	X	X	
ESR amd CRP	X	X	X	X	X	X	X	X	X	X	X	X	X	X	
Urinalysis f	X						As clin	nically in	dicated						
Coagulation parameters g	X						As clin	nically in	dicated						
Tumor assessment (CT or MRI); Bone Scan (99mTc)h	X	Xh		Xh		Xh		Xh		Xh		Xh		Xh	Section 9.0
PSA i	X	X	X	X	X	X	X	X	X	X	X	X	X	X	Section 9.3

<sup>a Full physical examination at day 1 of cycle 1; targeted physical examination at other time points. Body weight recorded at all physical examinations. Height is only measured at screening.

- At the beginning of the treatment administration infusion (at  $\pm 30$  minutes)
- Once during treatment administration
- At the end of treatment administration ( $\pm 30$  minutes)
- 60 minutes post-treatment administration: (±30 minutes) –if no clinically significant infusion reactions are observed during or after the first cycle, subsequent infusion observation and vital signs period can be conducted at the Investigator's discretion.

<sup>b Subjects will have their blood pressure and pulse measured before, during, and after the infusion at the following times (based on a total treatment infusion):

j: A minimum of two combination cycles are required. Subjects experiencing adverse events (AEs) related to combination dose therapy (Part 1) that do not meet dose discontinuation criteria, may proceed to durvalumab monotherapy dosing (Part 2) without completing all 4 combination doses, Additional durvalumab monotherapy doses will be given to complete 13 treatment cycles(up to 11 durbalumab monotherapy cycles).

<sup>c ECG during screening. Thereafter as clinically indicated. Baseline and abnormal ECG at any time in triplicate others single-infusion. (Clinically significant abnormalities detected require triplicate EKG's).

<sup>d If screening laboratory assessments are performed within 3 days prior to Day 1 they do not need to be repeated at Day 1. Results for safety bloods must be available and reviewed before commencing an infusion.

<sup>e Total T3 and free T4 will only be measured if TSH is abnormal. They should also be measured if there is clinical suspicion of an adverse event related to the endocrine system.

<sup>f Urinalysis performed at Screening, then as clinically indicated

<sup>g Coagulation tests: prothrombin time, APTT and INR – only performed at Screening and as clinically indicated.

b Free T3 and free T4 will only be measured if TSH is abnormal. They should also be measured if there is clinical suspicion of an adverse event related to the endocrine system.

<sup>C ESR and CRP should be collected for the first 3 follow-up visits (Day 30, Month 3)

<sup>d Survial status will be evaluated by phone /or in person at 30 day, 3 month and 12 month visit

### 8.1.2 End of Treatment

End of treatment is defined as the last planned dosing visit within the 12-month dosing period. For subjects who discontinue durvalumab or tremelimumab prior to 12 months, end of treatment is considered the last visit where the decision is made to discontinue treatment. All required procedures may be completed within  $\pm$  7 days of the end of treatment visit. Repeat disease assessment is not required if performed within 28 days prior to the end of treatment visit.

## 8.2 Biological sampling procedures

### **8.2.1** Correlative studies

The correlative studies will be obtained from patients participating other MD Anderson IRB approved biospecimen protocols.

Upon treatment completion, biospecimens available will be analyzed per each approved protocol. In addition, new technologies have been developed. Exosomes are vesicles secreted from cells and function as mediators of intercellular communication. They have been shown to play a key role in the cross-talk between the immune and non-immune components in the local and distant tumor microenvironment. Exosomes will be isolated from the plasma and bone marrow of patients, and molecular analyses will be performed, which will be associated with clinical outcomes.

## 8.2.2 Informed consent for donated biological samples

#### Withdrawal:

If a subject withdraws consent to the use of donated samples, the samples will be disposed of/destroyed, and the action documented. As collection of the biological samples is an integral part of the study, then the subject is withdrawn from further study participation.

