## 4.3 Withdrawal of Subjects from Study Treatment and/or Study

#### Permanent discontinuation of either durvalumab plus tremelimumab or durvalumab.

An individual subject will not receive any further investigational product if any of the following occur in the subject in question:

- 1. Withdrawal of consent or lost to follow-up.
- 2. Adverse event that, in the opinion of the investigator or the sponsor, contraindicates further dosing.
- 3. Subject is determined to have met one or more of the exclusion criteria for study participation at study entry and continuing investigational therapy might constitute a safety risk.
- 4. Any AE that meets criteria for discontinuation as defined in the Dosing Modification and Toxicity Management Guidelines (see Table 3).
- 5. Subject noncompliance that, in the opinion of the investigator or sponsor, warrants withdrawal; eg, refusal to adhere to scheduled visits.
- 6. Initiation of alternative anticancer therapy including another investigational agent.
- 7. Confirmation of PD and investigator determination that the subject is no longer benefiting from treatment with durvalumab + tremelimumab.
- 8. Withdrawal of consent from further treatment with IP. The patient is, at any time, free to discontinue treatment, without prejudice to further treatment. A patient who discontinues treatment is normally expected to continue to participate in the study unless they specifically withdraw their consent to further participation in any study procedures and assessments

Subjects who are permanently discontinued from further receipt of investigational product, regardless of the reason (withdrawal of consent, due to an AE, other), will be identified as having permanently discontinued treatment.

Subjects who are permanently discontinued from receiving investigational product will be followed for safety per Section 10.1 and Table 2, including the collection of any protocol-specified blood specimens, unless consent is withdrawn or the subject is lost to follow-up or enrolled in another clinical study. All subjects will be followed for survival. Subjects who decline to return to the site for evaluations will be offered follow-up by phone per the schedule in table 2 as an alternative.

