### 9.0 DISEASE EVALUATION AND METHODS

Imaging performed prior to informed consent may be used as baseline assessment if it was performed within 28 days prior to study drug administration. Scans should be scheduled in such a way that the scan results are available at the regularly scheduled visit.

CT or MRI scans will be performed every 8 weeks for the first 48 weeks and then every 12 weeks until confirmed PD.

Additional imaging may be performed at any time to confirm suspected progression of disease. Study films (abdominopelvic CT/MRI and bone scan) should be read on site. The principal investigator or a sub-investigator will evaluate the images for all subjects for the duration of the study.

The same imaging method used for an individual subjects at baseline should be used throughout the entire study for that subject, unless for medical reasons the method must be changed (e.g. inability to receive contrast agent).

If a subject is unable to return for restaging scans due to symptoms of progressive disease, he may have scans done by a local facility. These scans should be sent to the investigator for review.

PET scans should not be used to determine disease progression.

Radiographic evaluation of metastatic disease is determined separately for soft -tissue and bone disease.

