# 10.3 Study recording period and follow-up for adverse events and serious adverse events

Adverse events and serious adverse events will be recorded from time of signature of informed consent, throughout the treatment period and including the follow-up period (90 days after the last dose of durvalumab + tremelimumab).

During the course of the study, all AEs and SAEs should be proactively followed up for each subject. Every effort should be made to obtain a resolution for all events, even if the events continue after discontinuation/study completion.

If a subject discontinues from treatment for reasons other than disease progression, and therefore continues to have tumor assessments (per Table 2), drug or procedure-related SAEs must be captured until the patient is considered to have confirmed PD and will have no further tumor assessments.

The investigator is responsible for following all SAEs until resolution, until the subject returns to baseline status, or until the condition has stabilized with the expectation that it will remain chronic, even if this extends beyond study participation.

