### Post study events

After the subject has been permanently withdrawn from the study, there is no obligation for the investigator to actively report information on new AE or SAEs occurring in former studysubjects after the 90-day safety follow-up period for patients treated with durvalumab + tremelimumab. However, if an investigator learns of any SAEs, including death, at any time after the subject has been permanently withdrawn from study, and he/she considers there is a reasonable possibility that the event is related to study treatment, the investigator should notify the study sponsor and AstraZeneca/MedImmune Drug Safety.

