# 11.2.2 Efficacy analyses

Efficacy of this combination will be measured by PSA progression-free survival (PFS), radiographic PFS, and maximal decline of PSA from baseline. PSA PFS, radiographic PFS, and time to maximal PSA decline will start at the first day of treatment and will be summarized by Kaplan-Meier. The numeric PSA value at maximal decline will be summarized by a boxplot and as a scatter plot of maximal decline by baseline PSA.

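### Section 8.2.2 ends all study participation when a patient withdraws only his sample consent, which needlessly cuts short his clinical follow-up (minor, cheap to fix)

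*Combined protocol and SAP*

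**What the plan says.** Section 8.2.2, under Withdrawal, has a narrow trigger: the patient withdraws consent to the use of donated samples. Two consequences follow. The samples are destroyed, and "As collection of the biological samples is an integral part of the study, then the subject is withdrawn from further study participation". The list of investigator duties later in 8.2.2 concerns sample disposal only.

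Section 4.3 takes a different line on partial withdrawal. Under item 8, a patient who stops study drug is normally expected to remain in the study unless he specifically withdraws from further procedures and assessments. Patients taken off study drug are followed for safety "unless consent is withdrawn or the subject is lost to follow-up or enrolled in another clinical study". The next sentence reads "All subjects will be followed for survival".

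The follow-up that 8.2.2 would end feeds the efficacy summaries. Section 11.2.2 states: "Efficacy of this combination will be measured by PSA progression-free survival (PFS), radiographic PFS, and maximal decline of PSA from baseline". Section 9.0 sets the imaging schedule: "CT or MRI scans will be performed every 8 weeks for the first 48 weeks and then every 12 weeks until confirmed PD". Table 2, footnote d, adds: "Survial status will be evaluated by phone /or in person at 30 day, 3 month and 12 month visit".

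On safety, Section 10.3 has serious events followed to resolution or stability "even if this extends beyond study participation". For patients withdrawn from the study, its wording on reporting is: "no obligation for the investigator to actively report information on new AE or SAEs occurring in former studysubjects after the 90-day safety follow-up period". Section 10.4 captures serious events to 90 days after the last dose unless the participant withdraws consent.

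**The concern.** The trigger is narrow and the consequence has no limit. The stated reason, that samples are integral to the study, justifies dropping the patient from biomarker work. It does not explain why his scans and survival contacts should stop when he has not declined them.

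For a patient who already meets Section 11.1.2 (2 doses, markers measured, at least one clinical follow-up), the result is avoidable censoring of radiographic PFS, and of PSA PFS if he is still on treatment. If the decision to withdraw is related to how he is doing, the censoring is also informative. If his markers had not been measured, he is only described separately under 11.1.2, and that description is cut short. This second case is possible because Section 8.2.1 analyses specimens on treatment completion.

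Site staff are also left without a rule: 4.3 and 10.4 do not say whether withdrawal of sample consent counts as withdrawn consent.

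**Working it through.** The plan gives no figure on this point, so the check is a comparison of texts, followed by an estimate of size under stated assumptions.

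**1. Texts side by side.**
- 8.2.2: sample consent withdrawn, so all further participation ends. No exception is written.
- 4.3 item 8: treatment stopped, so participation normally continues unless the patient specifically withdraws from it.
- 4.3, survival sentence: covers all subjects and has no exception of its own. It closes a paragraph on patients taken off study drug, and the consent exception stands in an earlier sentence on safety follow-up and blood specimens.

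The mismatch with item 8 is clear. The tension with the survival sentence is real but softer.

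**2. What is lost after week 48.** The Waiver paragraph of 8.2.2 says that patients have completed the treatment phase, so this is the case that remains.
- Scans every 12 weeks until confirmed progression.
- Any remaining survival contacts (30 days, 3 and 12 months, then 6-monthly).
- No PSA tests, because Table 2 schedules none.

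Section 11.3 assumes that 75% (or 80%) of patients progress by the end of the study, without dating that end. Assume it means week 48. Then 20 × 0.25 = 5 patients (or 20 × 0.20 = 4) would still be due scans at week 48. If PFS is exponential and the curve is extended, the chance that one of them progresses by the next scan at week 60 is 1 − 0.25^(12/48) = 0.29 (or 1 − 0.20^(12/48) = 0.33). That is the follow-up information lost per patient over one scan interval.

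**3. What would be lost by withdrawal on treatment, just after the week-8 visit.** From Table 1: scans at weeks 16, 24, 32, 40 and 48, so up to 5; PSA tests at C4 to C13, so up to 10. The PSA tests exist only if he stays on treatment.

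With S(t) = 0.25^(t/48), t in weeks, a patient progression-free at t has a chance 1 − 0.25/S(t) of an event by week 48:
- t = 8: S = 0.794, giving 0.69
- t = 24: S = 0.500, giving 0.50
- t = 48: 0

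With 80% progression the first two become 0.74 and 0.55.

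**4. Precision of Kaplan-Meier PFS at week 48.** For n = 20 with k patients lost at week 8, the Greenwood variance is 0.25²/20 × [(1/0.794 − 1) + (1/0.25 − 1/0.794)/G]. Here G = 1 − k/15.9, and 15.9 = 20 × 0.794 is the expected number still at risk.

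| k | SE | 95% half-width (points) |
|---|---|---|
| 0 | 0.0968 | 19.0 |
| 1 | 0.0998 | 19.6 |
| 3 (assumed upper case) | 0.1066 | 20.9 |

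**5. Possible bias.** If withdrawal is related to outcome, the best-to-worst range for one unknown patient is 1/20 = 5.0 points.

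**The case against.** The strongest reply is that the rule is deliberate. Laboratory-protocol consent and serial sampling are entry criteria (Section 4.1, items 7 and 8), and evaluability for the secondary objectives requires measured markers. That stands as a reason to exclude the patient from biomarker work. It gives no reason to stop scans that he has not refused.

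Second, partial withdrawal is usually settled in the consent form, and the samples come from other biospecimen protocols. Neither text is in our copy. This stands as a limit: the consent form may already allow what is proposed here.

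Third, the study is a pilot with no formal hypotheses, the treatment phase is reported complete, and the week-8 figures describe a situation that has passed. This also stands, and it is why the point is minor.

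Three stronger readings are tempting, and the documents do not support them:
- *That 8.2.2 flatly contradicts the survival sentence in 4.3.* That sentence sits in a paragraph on patients off study drug, directly after an exemption for withdrawn consent. A fair reader could extend the exemption to survival, although the text does not do so.
- *That safety data are lost.* Sections 10.3 and 10.4 leave this unclear. The Section 10.3 text points towards continued follow-up, since the duty to report new events lapses only after 90 days.
- *That the CD3 Cox model loses power because of this rule.* If the samples are destroyed before measurement, or the marker data are removed, the model loses the patient whatever is decided about follow-up.

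**Conclusion.** The point holds as a minor one. As written, 8.2.2 ends clinical follow-up for a patient who has declined only sample use. This goes further than its own rationale supports and is out of line with 4.3 item 8.

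The size is small, and the frequency is not given in the documents. At present mainly the 12-weekly scans until progression and the survival contacts are affected. Section 11 specifies no overall survival analysis, so the survival loss is one of status data. A withdrawn patient still contributes his time at risk up to withdrawal.

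The week-8 figures (19.0 to 19.6 points with one patient lost, 20.9 with three) should be read as what the rule could have cost during treatment, not as its present effect. They rest on exponential PFS, on placing the plan's 75% progression at week 48, and on an assumed number of losses.

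**What to change.** In 8.2.2, state that withdrawing consent to sample use ends sample collection, sample use and biomarker evaluation only. Scheduled tumour assessments, AE/SAE follow-up to 90 days and survival contacts continue, as do PSA tests while he is on treatment, unless he separately declines them. He stays in the PFS summaries if he had already met 11.1.2; otherwise he is described separately.

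In 4.3 and 10.4, state that withdrawn consent does not include withdrawal limited to samples. Align the consent form if it differs. No rule on continuing study drug is proposed.

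The cost is one sentence, two short clarifications and a check of the consent wording. Samples are still destroyed, and the patient may still refuse follow-up. The downside is that a few patients may be followed without marker data, and those who had not met 11.1.2 add only to the separate description.
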